8.4 Safety reporting and medical management

8.4.1 Reporting of serious adverse events

All SAEs have to be reported, whether or not considered causally related to the study treatment, or to the study procedure(s). All SAEs will be recorded in the eCRF.

If any SAE occurs in the course of the study, then Investigators or other site personnel inform the appropriate AstraZeneca representatives within 1-day ie, immediately but **no later than 24 hours** of when he or she becomes aware of it.

The designated AstraZeneca representative works with the Investigator to ensure that all the necessary information is provided to the FibroGen Drug Safety **within 1 calendar day** of initial receipt for all SAEs. FibroGen Drug Safety will be responsible for processing all SAEs.

For fatal or life-threatening AEs where important or relevant information is missing, active follow-up is undertaken immediately. Investigators or other site personnel inform AstraZeneca representatives of any follow-up information on a previously reported SAE within 1 calendar day ie, immediately but **no later than 24 hours** of when he or she becomes aware of it.

The Investigator is obliged to report SAE to the appropriate local regulatory authorities, Ethics Committees and AstraZeneca representative within 24 hours of SAE awareness.

Safety information (SAEs, serious adverse drug reactions [SADRs], adverse drug reactions [ADRs] and suspected unexpected serious adverse reactions [SUSARS]) are to be reported by

Sponsor or Sponsor Representative to the appropriate local regulatory authorities within legally binding timelines.

Once the Investigators or other site personnel indicate an AE is serious in the electronic data capture (EDC) system, an automated email alert is sent to the designated AstraZeneca representative.

If the EDC system is not available, then the Investigator or other study site staff reports a SAE to the appropriate AstraZeneca representative by telephone.

The AstraZeneca representative will advise the Investigator/study site staff how to proceed.

For further guidance on the definition of a SAE, see [Appendix B](#) of the CSP.

8.4.2 Pregnancy

All pregnancies and outcomes of pregnancy should be reported to the AstraZeneca representative except for:

- If the pregnancy is discovered before the study patient has received any study treatment.

If a pregnancy is reported, the Investigator should inform the Sponsor representative within 24 hours of learning of the pregnancy.

Abnormal pregnancy outcomes (eg, spontaneous abortion, fetal death, stillbirth, congenital anomalies, ectopic pregnancy) are considered SAEs.

8.4.2.1 Maternal exposure

If a patient becomes pregnant during the course of the study, study treatment should be discontinued immediately.

Pregnancy itself is not regarded as an AE unless there is a suspicion that the study treatment under study may have interfered with the effectiveness of a contraceptive medication. Congenital abnormalities/birth defects and spontaneous miscarriages should be reported and handled as SAEs. Elective abortions without complications should not be handled as AEs. The outcome of all pregnancies (spontaneous miscarriage, elective termination, ectopic pregnancy, normal birth or congenital abnormality) should be followed up and documented even if the patient was discontinued from the study.

If any pregnancy occurs in the course of the study, then the Investigator or other site personnel informs the appropriate AstraZeneca representatives within 1 day ie, immediately but **no later than 24 hours** of when he or she becomes aware of it.

The designated AstraZeneca representative works with the Investigator to ensure that all relevant information is provided to FibroGen Drug Safety within 1 calendar day.

The same timelines apply when outcome information is available.

The PREGREP module in the eCRF is used to report the pregnancy and the PREGOUT form is used to report the outcome of the pregnancy.

8.4.2.2 Paternal exposure

Pregnancy of the patient's partners is not considered to be an AE. However, the outcome of all pregnancies (spontaneous miscarriage, elective termination, ectopic pregnancy, normal birth or congenital abnormality), occurring from the date of the first dose until at least 7 days after the last dose of roxadustat and as indicated by previous studies (pre-clinical and clinical) should, if possible, be followed up and documented in the Pregnancy Report Form. Consent from the partner must be obtained before the Pregnancy Report Form is completed and followed up as described in Section 8.4.2. To capture information about a pregnancy from the partner of a male patient, the male patient's partner consent must be obtained to collect information related to the pregnancy and outcome; the male patient should not be asked to provide this information.

8.4.3 Overdose

Refer to the respective China Package Insert for roxadustat and rHuEPO for information on the management of study treatment overdose.

AstraZeneca does not recommend specific treatment for an overdose.

- An overdose with associated AEs is recorded as the AE diagnosis/symptoms on the relevant AE modules in the eCRF and on the Overdose eCRF module.
- An overdose without associated symptoms is only reported on the Overdose eCRF module.

If an overdose on an AstraZeneca study treatment occurs in the course of the study, then the Investigator or other site personnel inform appropriate AstraZeneca representatives immediately, or **no later than 24 hours** of when he or she becomes aware of it.

The designated AstraZeneca representative works with the Investigator to ensure that all relevant information is provided to the FibroGen Drug Safety within 1 calendar day.

8.4.4 Medication error

Medication errors with AstraZeneca study treatment are collected in all studies where medication error is possible.

If a medication error occurs in the course of the study, then the Investigator or other site personnel initially reports to the appropriate AstraZeneca representatives within 1-day ie, immediately but no later than 24 hours of when he or she becomes aware of it.

The designated AstraZeneca representative will then work with the Investigator to ensure that all relevant information is completed within 1 calendar day.

The definition of a medication error can be found in [Appendix B](#).

8.5 Pharmacokinetics

Pharmacokinetic parameters are not evaluated in this study.

8.6 Pharmacodynamics

Pharmacodynamic parameters are not evaluated in this study.

8.7 Genetics

Genetic testing is not evaluated in this study.

8.8 Biomarkers

Biomarkers are not evaluated in this study.

8.9 Health economics

Health economics/medical resource utilization and health economics parameters are not evaluated in this study.

9 STATISTICAL CONSIDERATIONS

This section highlights statistical considerations for this CSP.

Individual data will be presented in patient listings. All patient data listings will be sorted by treatment, site, dialysis status and patient.

9.1 Statistical hypotheses

Statistical testing will be conducted at a 2-sided significance level of 5%. A multiple testing strategy will be used as described in Section 9.4.2.1. Where appropriate, model-based point estimates, together with their 95% confidence intervals (CIs) will be presented along with the 2-sided p-values for the tests.

9.1.1 Primary endpoint

The primary endpoint for this study is described in Section 8.1.1. This will be assessed via change from baseline (Day 1) at Day 15 in log-transformed AUC of iron absorption from

0-3 hours based on the change in serum iron levels obtained just prior to T0 (time when single dose of oral iron is administered) and over a 3-hour period. The hypothesis to be assessed is as follows:

H₀: There is no difference in the average change from baseline in the ferrokinetic measurement between rHuEPO and roxadustat.

$$\bar{d}_{rHuEPO} = \bar{d}_{roxa}$$

H_A: There is a difference in the average change from baseline in the ferrokinetic measurement between rHuEPO and roxadustat.

$$\bar{d}_{rHuEPO} \neq \bar{d}_{roxa}$$

Where \bar{d}_{rHuEPO} is the average change from baseline for the rHuEPO treatment group and \bar{d}_{roxa} is the average change from baseline for the roxadustat treatment group.

9.1.2 Secondary endpoints

The secondary endpoints of interest are described fully in Section 8.1.2. The hypotheses for these endpoints can be separated into 2 distinct groups, the relative difference in iron metabolism and the relative difference in AUC. All hypotheses will follow the null hypothesis that there is no difference between AUC or iron metabolism when adjusting for various specified covariates or interactions.

9.2 Sample size determination

CCI [REDACTED]

[REDACTED]

[REDACTED]

[REDACTED]

[REDACTED]

CCI [REDACTED]

[REDACTED]

9.3 Populations for analyses

For purposes of analysis, the following populations are defined:

Population	Description
All-patients analysis set	The all-patients analysis set will consist of all patients who are screened for the study. This analysis set will be used for listings.
Full analysis set	The full analysis set (FAS), the primary efficacy analysis set, will include all randomized patients who have who have complete baseline (Day 1) measurements for any efficacy analysis. The FAS will be used for the primary endpoint and all secondary endpoints. The FAS will also be used for the presentation of all demographic and disposition data.
Per-protocol analysis set	The per-protocol (PP) analysis set will include all randomized patients who received at least 1 dose of study treatment, have baseline (Day 1) and at least 1 post-baseline iron absorption measurement, and are without major protocol violations. Details for PP analysis set exclusion will be specified in the statistical analysis plan (SAP). The PP analysis set will be used as a sensitivity analysis population for the primary and secondary endpoints.
Safety analysis set	The safety analysis set will include all randomized patients receiving at least 1 dose of study treatment, with patients being analyzed as treated, rather than as randomized. The safety analysis set will be used for the safety endpoints. Exposure to study treatment will also be presented using the safety analysis set.

9.4 Statistical analyses

Analyses will be performed by Parexel. A comprehensive statistical analysis plan (SAP) will be developed and finalized before database lock and will describe the patient populations to be included in the analyses, and procedures for accounting for missing, unused, and spurious data. A stable SAP will be produced prior to first patient-in. This section is a summary of the planned statistical analyses of the primary, secondary and safety endpoints. Any deviations from this plan or the SAP will be reported in the CSR.

All efficacy and safety variables will be summarized by study treatment groups using descriptive statistics (n, mean, SD, median, minimum and maximum for continuous data and n, frequencies and percentages for categorical data, including proportion of missingness). Data will be summarized by visit, randomization strata and site as applicable.

Treatment and interaction effects will be evaluated via analysis of covariance (ANCOVA). All analyses will involve the difference of log-transformed AUC and indices of iron metabolism. Results can be presented on the untransformed scale for interpretability.

Multiple imputations will be implemented for the primary and secondary analyses to account for missing data, due to the increased risk of this occurring during the COVID-19 pandemic. This will be described in further detail in the SAP.

The statistical methods and how the variables are presented will be further detailed in the SAP.

9.4.1 Primary efficacy analyses

The primary efficacy endpoint is described in (Section 8.1.1). It is measured through change from baseline (Day 1) to Day 15 in log-transformed AUC of iron absorption from 0-3 hours based on the change in serum iron levels obtained just prior to T0 (time when single dose of oral iron is administered) and over a 3-hour period.

The AUC curve (for the calculation of the primary endpoint and associated secondary endpoints) will be determined for each patient at baseline (Day 1) and post-baseline, then the average of the changes from baseline (Day 1) will be evaluated for each treatment group. This is to be calculated for patient i as the sum of the area of each trapezium under the curve, adjusted for any iron present in sample obtained just prior to time T0. Let P_j be the serum iron level at timepoint T_j then the AUC for patient i at Visit X is

$$AUC_{X,i} = \sum_{j=0}^2 \left(\frac{P_{j+1} + P_j}{2} - P_0 \right)$$

Let d_i be the change from baseline for patient i and is defined as:

$$d_i = \log(AUC)_{Day\ 15,i} - \log(AUC)_{Baseline,i}$$

The difference in log (AUC) from baseline (Day 1) to Day 15 will be analyzed using an ANCOVA model, adjusting for study treatment and baseline hs-CRP level (\leq ULN, $>$ ULN).

If a patient withdraws before Day 15, their discontinuation visit will be used as the post-baseline primary measurement.

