Estimated date of first patient enrolled: Q1 2021

Estimated date of last patient completed: Q4 2021

Number of patients:

A maximum of 104 patients are planned to be screened to achieve a minimum of 20 and a maximum of 60 eligible randomized patients with anemia of CKD fulfilling all the inclusion criteria and none of the exclusion criteria.

The minimum sample size required to achieve a 2-sided significance level of 0.05 and power of 90% was calculated based on the assumption of a log scale. A conservative effect due to roxadustat has been assumed of 2.7-times baseline, and accounting for 20% of patients failing to take any study treatment or failing to provide a post-baseline area under the curve (AUC) measurement. A conservative estimate of the standard deviation (SD), based on the estimated range of iron absorption was 0.4 on the log scale. A sample size of 16-20 subjects (8-10 per treatment arm) is considered sufficient to achieve a 2-sided significance level of 0.05, and 90% power, based on the primary endpoint of change from baseline in log(AUC). Patients are to be randomized in a 1:1 ratio. The calculations are based on a 2-sample t-test.

Treatments and treatment duration:

Each patient will be contacted before the first Screening Visit (Visit 1) to confirm that he/she has no symptoms of coronavirus disease of 2019 (COVID-19) and that he/she has had no contact with a known COVID-19 positive person within the past 14 days. Only asymptomatic patients, or those who have had no contact with a known COVID-19 positive person within the last 14 days, will be asked to come to the site for informed consent and eligibility screening procedures.

For each patient, the duration of participation in the study will be approximately 8 to 9 weeks divided into 3 periods:

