2 INTRODUCTION

2.1 Study rationale

Advanced stages of chronic kidney disease (CKD) are associated with a hypo-proliferative anemia as well as dysfunctional iron homeostasis. The latter leads to functional iron deficiency, a process that describes multiple abnormalities in iron transport and utilization, including impaired gastrointestinal (GI) iron absorption. The latter appears to be mediated by paucity of hypoxia inducible factor (HIF)-2 α , a subunit of HIF which boosts intestinal absorption of iron by upregulating duodenal cytochrome b and divalent metal transporter.

The prevalence of anemia increased as CKD progresses. The prevalence of anemia has been found to increase with the stage of CKD; from 8.4% at Stage 1 to 53.4% at Stage 5 ([Stauffer and Fan 2014](#)).

The prevalence of CKD is about 10.8% in China ([Zhang et al 2012](#)). According to the 2011 Shanghai Dialysis Registry Report, the prevalence of end-stage renal disease (ESRD) is 759 per million Chinese; the prevalence has almost doubled in the last 4 years when compared to 2007, at which time the prevalence was estimated to be 409.8 per million (<http://sh.cnrds.org>).

While recombinant human erythropoietin (rHuEPO) has been able to correct anemia in many patients with CKD, it has not been demonstrated to correct underlying iron dysmetabolism associated with CKD. Iron dysmetabolism and impaired GI absorption of iron is a well-recognized clinical phenomenon and is extensively described in the literature ([Gupta and Wish 2017](#)). Recombinant human erythropoietin has not been demonstrated to correct this issue ([Widness et al 1997](#)).

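### The primary endpoint is the log of a baseline-subtracted AUC that can be zero or negative, and the protocol gives no rule for that case

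*Protocol*

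**What the plan says.** Section 9.4.1 defines the AUC at each visit as the "sum of the area of each trapezium under the curve, adjusted for any iron present in sample obtained just prior to time T0". In the formula, the pre-dose value P0 is subtracted from each of the three hourly trapezia. The patient-level endpoint is log(AUC) at Day 15 minus log(AUC) at Day 1. "The difference in log (AUC) from baseline (Day 1) to Day 15 will be analyzed using an ANCOVA model", with treatment and hs-CRP category (at or below ULN, above ULN) as the only terms. Baseline AUC is not a covariate. Section 9.4.2 also log-transforms the AUC for the secondary models.

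Section 9.3 admits to the full analysis set every randomized patient with complete Day 1 measurements; a positive AUC is not required. For absent values, Section 9.4 says "Multiple imputations will be implemented for the primary and secondary analyses to account for missing data", gives COVID-19 as the reason, and leaves detail to the SAP. No offset, floor or other rule for AUC ≤ 0 is stated.

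On what to expect, Section 2.1 describes functional iron deficiency in advanced CKD as involving "multiple abnormalities in iron transport and utilization, including impaired gastrointestinal (GI) iron absorption", and Section 4.2 takes rHuEPO to have little effect on absorption. The synopsis sizes the trial on the log scale: "A conservative effect due to roxadustat has been assumed of 2.7-times baseline", SD 0.4, 8 to 10 per arm, with 20 to 60 patients to be randomized.

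**The concern.** Subtracting P0 makes the AUC a noisy difference that may be zero or negative, and a log cannot take such values. A flat curve from four valid samples is a measured finding of no detectable absorption, yet the endpoint has no value for it. An AUC just above zero has a value, but one so negative that it can outweigh the other patients in a small arm.

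Given Sections 2.1 and 4.2, low AUCs are foreseeable at Day 1 in both arms and at Day 15 mainly under rHuEPO. The affected values would then depend on the outcome and differ by arm. In an open-label trial, an unstated rule also leaves room for a choice made after the data are seen. At stake are the computability of the primary endpoint and the power at the planned minimum size.

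**Working it through.** **1. The plan's sample size.** The effect is ln(2.7) = 0.993, with two-sided 5%, 90% power and a two-sample t-test.
- SD 0.4 read as the SD of the change: 5 per arm, or 5/0.8 = 6.25, so 7 after the 20% allowance. This does not match.
- SD 0.4 read as the SD at one visit with uncorrelated visits: SD of change 0.4·√2 = 0.566, giving 8 per arm (power 90.4%) and 8/0.8 = 10.

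The second reading reproduces 8 to 10 per arm, so the stated size is not in error. It does need log(AUC) to be well behaved: at an SD of change of 0.8 or 1.0, power at 8 to 10 per arm is 64–75% or 46–56%.

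**2. The formula.** (P0+P1)/2 + (P1+P2)/2 + (P2+P3)/2 − 3·P0 = P1 + P2 + 0.5·P3 − 2.5·P0. Illustrative profiles (P0, P1, P2, P3):
- 60, 90, 130, 140 gives 140
- 60, 61, 60, 59 gives 0.5
- 60, 60, 60, 60 gives 0 (log undefined)
- 60, 58, 57, 59 gives −5.5 (log undefined)

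**3. Noise.** The squared weights sum to 6.25 + 1 + 1 + 0.25 = 8.5. With an assumed per-sample SD of 8 µg/dL, the noise SD of the AUC is 8·√8.5 = 23.3 µg·h/dL.

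**4. One extreme value.** An AUC of 1 where 60 is typical shifts an 8-patient arm mean by ln(60)/8 = 0.51, half the planned effect. At SD of change 0.566, one roxadustat value 10-fold too low cuts t-test power from 90% to about 32% (8 per arm) or from 96% to about 57% (10 per arm). A rank-sum test on such data keeps about 56% and 76%. At 30 per arm both tests stay above 99%.

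**5. Frequency and power under assumptions.** The protocol gives no serum iron values. Assumed: 8 per arm, true 2.7-fold effect, between-patient log SD 0.4, within-patient correlation 0.5, per-sample SD 8 µg/dL, undefined values dropped from the log analyses.

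| Median AUC (µg·h/dL) | Trials with an undefined value | Log-change t-test | Log ANCOVA with baseline log(AUC) | Untransformed ANCOVA with baseline AUC |
|---|---|---|---|---|
| 100 | 6% | 92% | 99% | 99% |
| 60 | 38% | 74% | 94% | 95% |
| 30 | 94% | 35% | 60% | 81% |

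Rank-based ANCOVA gives 99%, 96% and 79%. The trial-level rates follow from the rate per test at untreated absorption (16 Day 1 tests plus 8 rHuEPO Day 15 tests). At 2% per test, 1 − 0.98^24 = 38%; at 11%, 1 − 0.89^24 = 94%.

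**6. Sensitivity.**
- Median AUC 60, 8 per arm: a per-sample SD of 5 gives 90% power with 8% of trials affected; an SD of 3 gives 98% and 0.4%.
- 30 per arm, SD 8: power is 99% at median 60 and 87% at median 30. Undefined values do not go away: at 2% per test over 90 such tests, 1 − 0.98^90 = 84% of trials have one.
- A wider assumption set (median P0 70 µg/dL, median 3-hour rise 10–80 µg/dL, between-patient log SD 0.5–0.8, measurement CV 5–10%) puts the rate per visit anywhere from about 0.01% to 20%.

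**The case against.** The strongest reply is that a rule for AUC ≤ 0 is ordinary SAP content, and the SAP is not at hand. That stands in part, since an SAP could supply a floor or an offset. But the protocol fixes both the formula and the log, so an SAP could only substitute for or exclude the affected values, and a flat curve from valid samples is an observed result, not missing data.

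Four stronger readings are tempting and not supported:
- *Non-absorbers will be imputed as if they absorbed.* The protocol never says so. Imputation is its only stated mechanism for an absent value, and the model is not described.
- *The population is selected for poor absorption, so flat curves are the norm.* No criterion in Sections 5.1 or 5.2 concerns absorption. Bowel resection, coeliac disease and recent gastroenteritis are excluded, and minimum ferritin and TSAT are required. Section 2.1 is background on the disease.
- *The planned power is lost.* That depends on assumed iron values, assay noise and a small trial. The plan allows 10 to 30 per arm, and 8 is the completer count at the minimum size.
- *The treatment contrast is biased.* With undefined values dropped, the simulated mean contrast was 0.97 to 1.06 against a true 0.99. Bias under imputation would depend on the unseen model.

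It is also fair that the log suits a multiplicative effect, and that comparing an unadjusted log t-test with a baseline-adjusted raw ANCOVA exaggerates the cost of the log. At median AUC 60, adjusting for baseline closes nearly all the gap (94% against 95%); at 30 a gap remains (60% against 81%). The heavy weight on P0 (6.25/8.5 = 74% of the noise variance) applies equally to the untransformed AUC and is no argument against the log.

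**Conclusion.** The point holds as a defect in a stated formula: the primary endpoint is undefined for an observed flat or falling curve and unstable for a small positive AUC, and the protocol has no rule for either. That much follows from Section 9.4.1 alone.

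The size does not. Under the assumptions shown, the consequence runs from negligible (low assay noise or high AUC) to severe (median AUC 30, 8 per arm). At 30 per arm the power loss is small except at low AUC, though undefined values remain. This should be fixed before the data are seen. The material does not show that the log endpoint must be abandoned; replacing it outright is partly a matter of preference.

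**What to change.** In Section 9.4.1:
1. State that AUC ≤ 0 from valid samples is an observed result, never treated as missing and never imputed.
2. Add baseline AUC as a covariate, on the scale of the analysis.
3. Pre-specify an analysis defined for every patient with valid samples at both visits: rank-based ANCOVA of Day 15 AUC on baseline AUC, or ANCOVA on untransformed AUC. Make it primary, or at least a named sensitivity analysis.
4. If the log ratio stays primary, set AUC ≤ 0 and very small AUCs at either visit to a pre-specified floor tied to assay precision. An arbitrarily small floor would recreate the extreme values shown in step 4 of the working.

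Keeping the log ratio primary needs only wording in Section 9.4.1 and the SAP. Making a rank-based or untransformed analysis primary costs more: it gives no directly back-transformed ratio, Sections 1.2, 3, 8.1.1 and 9.1.1 need aligned wording, and the log-scale sample size rationale should be revisited.

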9.4.2 Secondary efficacy analyses

The secondary efficacy endpoints for this study are outlined in Section 8.1.2.

The secondary endpoints of interest assess direct treatment and interaction effects in the indices of iron metabolism (ie, serum iron, ferritin, TIBC, TSAT, transferrin, soluble transfer receptor) and hepcidin levels are described in Table 5. All endpoints will be analyzed using ANCOVA models.

Table 5 Summary of secondary endpoints to be analyzed

Outcome of interest	Adjusted for	Variable(s) to be assessed
Relative difference in AUC ^a	Study treatment Baseline hepcidin value	Treatment effect Treatment-hepcidin interaction
Relative difference in AUC ^a	Study treatment Baseline hs-CRP value	Treatment effect Treatment-hs-CRP interaction
Relative difference in indices of iron metabolism ^b	Study treatment Baseline hs-CRP level (\leq ULN, $>$ ULN)	Treatment effect
Relative difference in indices of iron metabolism ^b	Study treatment Baseline hepcidin value	Treatment effect Treatment-hepcidin interaction
Relative difference in indices of iron metabolism ^b	Study treatment Baseline hs-CRP value	Treatment effect Treatment-hs-CRP interaction

^a The absorption of iron over a 3-hour period, measured just prior to T0 and at T1, T2, T3.

^b Indices of iron metabolism (ie, serum iron, ferritin, TIBC, TSAT, transferrin, soluble transferrin receptor, and hepcidin levels). These will be laboratory serum measurements.

AUC=area under the curve; hs-CRP=high sensitivity C-reactive protein; TIBC=total iron binding capacity; TSAT=transferrin saturation, ULN=upper limit of normal.

These secondary endpoints will be analyzed using ANCOVA models, similar to that described in [Table 5](#). The outcome variables (indices of iron metabolism and AUC) are to be log-transformed prior to analysis and the result back-transformed to the original scale to aid interpretability. Log-transformed baseline hepcidin and log-transformed baseline hs-CRP are to be used as covariates. The results will be back transformed to the original scale to aid interpretability.

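### The primary model omits baseline log(AUC), giving up precision by an amount that depends on an undocumented within-patient correlation; the analysis stays valid

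*Protocol*

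**What the plan says.** Section 9.4.1 defines the outcome for each patient as log(AUC) at Day 15 minus log(AUC) at baseline. This difference "will be analyzed using an ANCOVA model, adjusting for study treatment and baseline hs-CRP level", with hs-CRP split at the upper limit of normal. The Synopsis (Section 1.2) and Section 8.1.1 give the same two terms. None of the three places enters baseline log(AUC).

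For the secondary endpoints, Section 9.4.2 says: "These secondary endpoints will be analyzed using ANCOVA models, similar to that described in" Table 5. The two AUC rows adjust for baseline hepcidin or baseline hs-CRP, each with its treatment interaction. The iron-index rows adjust for hs-CRP category, baseline hepcidin, or baseline hs-CRP. An outcome's own baseline appears only for hepcidin, in the row that adjusts for baseline hepcidin.

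The protocol leaves multiple imputation and further method detail to the SAP, but it states these covariate lists itself. The SAP was not available for this check.

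**The concern.** The model is called an ANCOVA, but the outcome's own baseline is missing from it. It is a change-score analysis, which fixes the slope on baseline log(AUC) at 1 instead of estimating it. Two things follow.

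- **Precision.** Unless the two visits are highly correlated, a change score has a larger variance than an estimate adjusted for baseline.
- **Sensitivity to the observed baseline.** If the arms differ by chance in mean baseline log(AUC), the change-score estimate absorbs part of that difference.

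Both matter most in a small trial. The current protocol allows as few as 20 randomized patients. With the stated 20% loss, that leaves about 8 evaluable per arm.

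**Working it through.** **Inputs from the Synopsis.**
- Error rates: "2-sided significance level of 0.05 and power of 90" percent.
- Effect: "A conservative effect due to roxadustat has been assumed of 2.7-times baseline". On the natural log scale (assumed), ln(2.7) = 0.993.
- SD: the estimate "based on the estimated range of iron absorption was 0.4 on the log scale". The Synopsis does not say whether this is a single-visit SD or the SD of the change.
- Loss: "accounting for 20% of patients failing to take any study treatment or failing to provide a post-baseline area under the curve (AUC) measurement".
- Allocation and test: "Patients are to be randomized in a 1:1 ratio"; "The calculations are based on a 2-sample t-test".
- Stated size: 16–20 in total, 8–10 per arm.

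**Reproducing the stated size** (two-sample t-test, noncentral t).
- If 0.4 is a single-visit SD and the visits are uncorrelated, the SD of the change is 0.4 × √2 = 0.566. Then 8 per arm gives 90.4% power, and 8 / 0.8 = 10 per arm. This matches 16–20.
- If 0.4 is the SD of the change, 5 per arm suffice, and 5 / 0.8 = 6.25 rounds up to 7 per arm (14 in total). Power at 8 per arm is 99.6%.

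The first reading fits better, but it does not show that the sponsor assumed r = 0. Section 9.2 is redacted.

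**Variance comparison.** Let s be the single-visit SD, equal at both visits, and r the within-patient correlation.
- Change score: variance proportional to 2s²(1 − r).
- Baseline-adjusted: variance proportional to s²(1 − r²).
- Large-sample ratio: (1 + r)/2.

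Estimating the baseline slope has a cost at 8 per arm. The simulated ratios below have a binary hs-CRP term in both models, assumed unrelated to baseline AUC.

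| r | (1 + r)/2 | Simulated ratio, 8 per arm |
|---|---|---|
| 0 | 0.50 | about 0.54 |
| 0.25 | 0.63 | about 0.68 |
| 0.5 | 0.75 | about 0.8 |
| 0.7 | 0.85 | about 0.92 |
| 0.9 | 0.95 | slightly above 1 (about 1.04) |

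**Power at 8 evaluable per arm**, same simulation, s = 0.4 read as a single-visit SD:

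| True effect | r | Planned model | With baseline log(AUC) |
|---|---|---|---|
| 2.0-fold | 0 | about 60% | about 84% |
| 2.0-fold | 0.25 | about 72% | about 86% |
| 1.75-fold | 0.5 | about 71% | about 79% |

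At the assumed 2.7-fold effect, the planned model has about 87% power at r = 0 by simulation (90% by noncentral t) and about 99% at r = 0.5. The 2.0-fold and 1.75-fold effects are illustrations; the protocol does not state them.

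**Observed baseline difference.** Given a difference D in mean baseline log(AUC), the change-score estimate shifts by −(1 − r) × D. Simulated slopes at 8 per arm were −1.02, −0.69, −0.52 and −0.30 at r = 0, 0.3, 0.5 and 0.7; the adjusted estimate had a slope of about 0. With s = 0.4 the SD of D is 0.4 × √(2/8) = 0.20. At r = 0.5, a one-SD difference shifts the estimate by 0.5 × 0.20 = 0.10 log units, and exp(0.10) = 1.105, about 10% on the ratio. Averaged over randomization both estimators were unbiased: simulated means were about 0.99 against a true 0.993.

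**The case against.** The best defence is that nothing here is invalid and the planned power holds. That largely stands. A change score in a randomized trial is unbiased, its test keeps its level, and its confidence interval already reflects chance imbalance. At the protocol's own 2.7-fold effect, power is close to 90% in the least favourable case ranged here (r = 0). Eight per arm is also the floor, since up to 60 patients may be randomized; at 30 evaluable per arm, simulated power for both smaller effects exceeds 99% without the covariate.

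A reader might infer that half the efficiency is lost. That needs r = 0, and the documents give no correlation. A reader might also infer that the change score is worse whenever r is below 1. At 8 per arm this is false: above about r = 0.85 the adjusted model is slightly worse. Strong regression to the mean in this test is plausible, but no repeatability data are given. Stratified randomization would reduce baseline imbalance if AUC differs by stratum, so the 0.20 above may be too high.

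The full analysis set wording may not guarantee a baseline AUC in every patient, and a pre-dose-corrected AUC can be zero or negative, leaving its log undefined. Neither point argues against the covariate, because a patient without baseline log(AUC) has no observed change score either.

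The defence gives no reason to leave the term out. The possible loss is trivial and the possible gain is material.

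**Conclusion.** The omission is certain as the protocol stands: three descriptions of the primary model agree on treatment and hs-CRP category only. Its cost is lost precision, lower power for effects smaller than assumed, and sensitivity to the observed baseline difference. The amount is unknown because r is undocumented. At 8 evaluable per arm, adding the covariate cuts the variance by nearly half at r = 0, about a fifth at r = 0.5 and less than a tenth at r = 0.7, with no gain at 0.9. These figures assume equal variances at the two visits and hs-CRP category unrelated to baseline AUC; the power figures also assume that 0.4 is a single-visit SD. The documents do not support reading this as bias, an inflated error rate, or a failure of the planned power.

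**What to change.** In the Synopsis, Section 8.1.1 and Section 9.4.1, add baseline log(AUC) as a continuous covariate beside treatment and hs-CRP category. Do the same in both AUC rows of Table 5. For each iron index, add the log-transformed baseline of that index to its own models where it is not already present; the hepcidin outcome already has it in the baseline-hepcidin row. Carry the same wording into the SAP.

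With the covariate in the model, the treatment estimate is the same whether the outcome is the change or the Day 15 log(AUC), so the endpoint definition need not change.

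The cost is one degree of freedom per model, a trivial loss of precision if r is above about 0.85, and no new data, since the Day 1 ferrokinetic study is completed before randomization. The Table 5 interaction models already estimate four parameters (intercept, treatment, covariate, interaction), so the extra term is felt a little more there.
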